16.3.3 Principal Investigator responsibilities

There will be legal data transfer agreements between the UNEXE and the site Universities in Gent, Valencia and Munich and MSS and AUD. Each site is also a grant holder rather than just a site so has committed to uphold the standards outlined in the EU document and in the protocol.

16.4 Schedule of Procedures

Table 16 The Schedule of Procedures

Procedures	Screening	Baseline (at same time as screening)	1 month Follow Up	3 month follow up	12 month follow up
Informed consent	Yes	Yes	Yes	Yes	Yes
Further Demographics	DOB Gender	Occupation Education level	Occupation DOB	Occupation DOB	Occupation DOB
Mental Health History	Yes	No	No	No	No
Current Physical conditions	No	Yes	No	Yes	Yes
Current medications	No	Yes	No	Yes	Yes
Eligibility assessment	Yes	No	No	No	No
Randomisation	No	Yes	No	No	No
Access to intervention	No	No	Yes	Yes	Yes
Compliance with intervention	N/A	N/A	No*	No	No
Assessment of wellbeing and depression	Y	N	Y	Y	Y
Assessment of emotional competence	Ν	Y	Y	Y	Y
Assessment of current functioning	N	Y	Y	Y	Y
Assessment of service use	N	Y	N	Y	Y
Adverse event assessments	N	N	Υ	Y	Y

*There are App notifications to the ppt to aid compliance and there is summary reporting of compliance, but no specific check at follow up as this would break blind

16.5 Safety Reporting Flow Chart

Safety Flow Chart Version 1

AE reported on screener follow up. CTU website logs all AE and reported reasons

Website sends alert to site PI, site researcher and trial manager if AE reported and ppt ticks that its related to trial participation AE reported to site Researcher via email or phone, Risk log to be completed and submitted to site PI within 2 days.

AE Monitoring

All sites to produce end of monthly report of AE/SAE, unblindings and protocol violations to trial manager

Site researcher attempts to contact ppt within 2 days to find out more if insufficient data to complete risk log

Trial manager to review site reports and CTU websites log of AE/SAE at the end of every month and provide monthly report for CI and DMEC representative /

If SAE reported to site Researcher via email or phone or website alert Risk log to be completed (contacting ppt if necessary) and submitted to site PI, trial manager and CI within 2 working days.

> If SAE reported to CI TM/CI informs the sponsor, steering committee and DMEC within 2 working days of event being reported

If serious concerns for patient wellbeing/scientific rigor then discussion with ethics committee within 7 days of event being reported

SAE check-AE questions to be asked at follow up, or if reported to the site researcher by phone/email: Have you experienced any health emergencies, accidents, unplanned hospital admissions in the last 3 months? What happened? (please describe) What caused this? Please tick all that apply Sports injury Traffic accident Assault Self injury Taking part in the trial Physical illness Work Other please state

AE check-Overall, has taking part in the trial so far made you feel much worse.....no effect.....much better? Please give details Have you had any problems with the App. If yes please give details:

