9.1 Definitions

Standard definitions for adverse events etc are in the table below.

Because the current interventions are digital self-help rather than a medicinal product and involve no biological agent, it is not appropriate to define adverse events etc re any untoward medical occurrence – rather as a psychological intervention, appropriate adverse events would include those related to mental state and behaviour including death, suicide attempt, self-harm, serious accident or violent incident, referral to crisis care or admission to psychiatric hospital. The following definitions are therefore adapted in light of this.

Term	Definition
Adverse Event (AE)	Standard: Any untoward medical occurrence in a participant to whom a medicinal product has been administered, including occurrences which are not necessarily caused by or related to that product.
	Adapted: Any deterioration in mental state or behaviour in a participant to whom the intervention has been administered, including occurrences which are not necessarily caused by or related to the intervention.
Adverse Reaction (AR)	Standard: An untoward and unintended response in a participant to an investigational medicinal product which is related to any dose administered to that participant.
	The phrase "response to an investigational medicinal product" means that a causal relationship between a trial medication and an AE is at least a reasonable possibility, i.e. the relationship cannot be ruled out.
	All cases judged by either the reporting medically qualified professional or the Sponsor as having a reasonable suspected causal relationship to the trial medication qualify as adverse reactions.
	Adapted: An untoward and unintended response in a participant to an intervention which is related to any dose of the intervention administered to that participant.
	The phrase "response to an intervention" means that a causal relationship between an intervention and an AE is at least a reasonable possibility, i.e. the relationship cannot be ruled out.

Table 15 Definitions of Events

	All cases judged by either the reporting appropriately clinically qualified professional or the Sponsor as having a reasonable suspected causal relationship to the intervention qualify as adverse reactions.

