9.3 Recording and reporting of SAEs, SARs AND SUSARs

All serious adverse events that are trial or treatment related will be recorded and immediately reported to the Chief Investigator and within 2 working days to the trial sponsor. If these are also classed as unexpected they will be reported to the relevant ethics committees. We will, in line with other complex intervention studies, monitor non-serious adverse events, serious adverse events that are not trial or treatment related, serious deterioration, and active withdrawals from treatment, with specific questions in the follow-up and in response to specific participant-initiated reports. Symptoms of depression or anxiety will not be defined as adverse events unless suicidal ideation, plans or an attempt has been made. The reporting period for all events and reactions will be from referral to 12month post baseline follow-up. Data on any adverse events will be collected by a member of the research team at each assessment.

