9.4 Responsibilities

Researchers at each trial site to check for AEs and ARs when participants complete digital treatment / follow-up, potentially in response to automated feedback from website

- 1. Principal Investigator (PI) for each trial site is responsible via liaison with research team at trial site for: Ensuring that all SAEs are recorded and reported to the sponsor within 2 working days of becoming aware of the event and provide further follow-up information as soon as available. Ensuring that SAEs are chased with Sponsor if a record of receipt is not received within 2 working days of initial reporting.
- 2. Ensuring that AEs and ARs are recorded and reported to the sponsor in line with the requirements of the protocol.
- 3. Immediate review of all SUSARs.
- 4. Review of specific SAEs and SARs in accordance with the trial risk assessment and protocol as detailed in the Trial Monitoring Plan.

Sponsor (NB where relevant these can be delegated to CI and trial manager)

- 1. Central data collection and verification of AEs, ARs, SAEs, SARs and SUSARs according to the trial protocol onto a database.
- 2. Reporting safety information to the CI, delegate or independent clinical reviewer for the ongoing assessment of the risk / benefit according to the Trial Monitoring Plan.
- 3. Reporting safety information to the independent oversight committees identified for the trial (Data Monitoring Ethics Committee (DMEC) and / or Trial Steering Committee (TSC)) according to the Trial Monitoring Plan.
- 4. Expedited reporting of SUSARs to the Competent Authority (MHRA in UK) and REC within required timelines.
- 5. Notifying Investigators of SUSARs that occur within the trial.
- 6. Preparing standard tables and other relevant information in collaboration with the CI and ensuring timely submission to the MHRA and REC.

Trial Steering Committee

In accordance with the Trial Terms of Reference for the TSC periodically reviewing overall safety data to determine patterns and trends of events, or to identify safety issues, which would not be apparent on an individual case basis.

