#### 6.10 Adverse events

The main anticipated adverse event in this trial is deliberate self-harm. Serious adverse events will be reported descriptively by treatment arm, also the number of participants in each treatment arm who have experienced at least one serious adverse event will be reported. Inferential analyses will also be performed using the count of events (Poisson or negative binomial model) and the number of participants experiencing the outcome at least once during the 12-month follow-up period (logistic regression), using observed data on an ITT principle with adjustment for covariates as for the outcome data analyses (Table A.14).

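### The adverse-event alert on the follow-up website depends on the participant attributing the event to the trial, so an SAE with no such tick and no current suicide-risk answers can stay in the log until month end

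*Protocol*

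**What the plan says.** Protocol 16.5 describes what happens when an event is entered on the follow-up website. Every entry is kept ("CTU website logs all AE and reported reasons"), but the alert is conditional: "Website sends alert to site PI, site researcher and trial manager if AE reported and ppt ticks that its related to trial participation". The log is otherwise picked up once a month: "Trial manager to review site reports and CTU websites log of AE/SAE at the end of every month". The expedited step has its own list of triggers: "If SAE reported to site Researcher via email or phone or website alert Risk log to be completed", with submission to the site PI, trial manager and chief investigator within 2 working days. A log entry without an alert is not on that list.

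The SAE check question in 16.5 looks back 3 months and asks about emergencies, accidents and unplanned admissions. It is followed by cause boxes of which several may be ticked. Self injury and taking part in the trial are separate boxes.

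Three parts of section 9 bear on this:

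- Section 9.4 makes the site PI responsible for "Ensuring that all SAEs are recorded and reported to the sponsor within 2 working days of becoming aware of the event".
- Section 9.3 sets a similar limit for a smaller class: "All serious adverse events that are trial or treatment related will be recorded and immediately reported to the Chief Investigator". For this class the limit for telling the sponsor is again 2 working days. Unrelated SAEs are to be monitored, with no such limit.
- Section 9.1 counts as adverse reactions "All cases judged by either the reporting appropriately clinically qualified professional or the Sponsor as having a reasonable suspected causal relationship to the intervention", and treats a link as reasonably possible if it cannot be ruled out.

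SAP 6.10 states: "The main anticipated adverse event in this trial is deliberate self-harm".

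**The concern.** Follow-up is online by default, and SAP 3.9 expects contact between participant and researcher only in particular circumstances. The website is therefore an important route by which an SAE becomes known. An alert that depends on attribution means the participant, not a clinician or the sponsor, decides which events are looked at promptly.

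The event that the SAP names as the main anticipated harm is one that a participant could naturally record as self injury without also ticking the trial box. SAP 3.6 plans no interim analysis for harms and no formal stopping guideline. Event review by the TSC and DMEC is the safeguard, and it works only as fast as events reach it.

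**Working it through.** The plan gives no figure to reproduce. The check is a trace through the reporting routes, followed by two small counts.

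**Trace.** Take a participant admitted to hospital after self-harm six weeks before the 3-month follow-up, with no suicidal thoughts at follow-up, who ticks only the self-injury box. Inpatient admission makes this an SAE under section 9.1.

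1. Adverse-event alert (16.5): needs the trial tick. Not sent.
2. Suicide-risk report (Appendix 16.1, follow-up website): needs PHQ-9 item 9 scored 1 to 3 and a yes to one of three further questions, all covering the last 2 weeks. Not sent. When it is sent, it carries the answers to those three questions, not the admission.
3. Notice to the site of elevated symptoms (Appendix 16.1, participants in the trial): no trigger is defined there. The examples in the adverse-events chapter are a PHQ-9 score above 20 or reported suicidal ideation. Neither applies.
4. Hospital questions in the AD-SUS: no alert is described.
5. Site check for adverse events at follow-up (9.4): planned, but with no deadline, and possibly prompted by the same website feedback.
6. Email or telephone: only if the participant makes contact or is telephoned.
7. Log: reviewed at month end.

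So no stated route with a deadline reaches this SAE before the month-end review.

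**Wait until month end.** With entries spread evenly over a 30-day month, the mean wait is 30 / 2 = 15 calendar days. A day-by-day count over 1 October 2020 to 30 September 2022 (730 days) took the review to be on the last working day of the month, left out weekends and ignored public holidays:

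| Quantity | Result |
|---|---|
| Mean wait, calendar days | 14.7 |
| Longest wait, calendar days | 32 |
| Mean / median wait, working days | 10.5 / 10 |
| Range, working days | 0 to 22 |
| Entry dates waiting more than 2 working days | 87% |

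These figures assume that nobody notices the entry sooner. If it were picked up in a weekly look at the database, the mean wait would be 7 / 2 = 3.5 calendar days.

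**Extra alerts if any yes triggers one.** Inputs are the revised total of 3599 (SAP 6.9), 60% response at 3 months (the complement of the 40% attrition in the sample-size sections) and an assumed yes rate of 2% to 10%.

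- Respondents: 0.60 × 3599 = 2159.
- Alerts: 0.02 × 2159 = 43 to 0.10 × 2159 = 216, or on average about 11 to 54 for each of the four sites.

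**The case against.** The strongest reply is that the flow chart is not the only safeguard.

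- The suicide-risk report and the elevated-symptom notice need no attribution. They would flag a participant who is still suicidal or severely distressed.
- Protocol 13.7 has the trial manager opening the database typically at least weekly, and 11.1 describes central monitoring in real time.
- Section 9.3 has a team member collecting adverse-event data at each assessment. The adverse-events chapter provides clinician input and a form to the DMEC and sponsor for concerns raised in assessments.

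All of this stands. A reader might infer that a self-harm admission reaches nobody until month end, and the documents do not support that. What remains is that none of these routes names the un-ticked SAE or sets a time limit for it. The database checks are for recruitment, data quality and process, not SAE review.

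A reader might also infer a breach of a protocol-wide 2-day rule. That goes too far. Only 9.4 covers all SAEs, while the filter in 16.5 resembles 9.3. The limit in 9.4 runs from awareness, and the documents do not say whether an unread log entry counts as awareness. 16.5 counts instead from the event being reported.

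Nor does the participant settle relatedness for good. All events enter the monthly report, the adverse-events chapter sends them to the DMEC and ethics committee for that judgement, and SAP 6.10 analyses SAEs by arm without an attribution filter. The tick affects speed, not final classification or analysis.

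Lastly, 16.5 is a chart whose arrows are not visible in the text, so the links between boxes are inferred. The sentences relied on are complete.

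**Conclusion.** The point holds for a defined group: SAEs entered on the website with no trial tick and no current suicide-risk answers. For these, 16.5 specifies only logging and month-end review, and the 2-working-day step does not start. The wait averages about 15 calendar days and can reach 32, provided that entries are evenly spread and nobody sees them earlier.

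This does not fit 9.4 or the allocation of the relatedness judgement in 9.1, and 9.3 and 9.4 disagree on which SAEs are expedited. Even if 9.3 is the intended rule, it can be applied in time only if a qualified person sees the event before relatedness is decided.

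A reader might go on to infer that prompt SAE information would differ between arms because self-monitoring participants blame the trial less often. Nothing in the documents supports that, and the point does not need it. No estimate or test is biased and no formal stopping rule depends on the alert. This should be fixed for the sake of safety oversight, but it does not threaten the trial's analysis.

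**What to change.** - In 16.5, trigger the website alert on any yes to the SAE check question, whatever cause is ticked, and treat that alert as the start of the 2-working-day step.
- Keep the cause boxes as information only, with relatedness judged as 9.1 provides.
- Reconcile 9.3, 9.4 and 16.5, together with the two risk alerts in Appendix 16.1, on which SAEs are expedited, what triggers an alert and when the clock starts. State whether a website entry counts as awareness.

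The cost is one changed alert condition in the survey and CTU system, a few sentences of protocol text, and extra triage of injuries and illnesses. The 43 to 216 alerts calculated above are for the 3-month assessment alone. The schedule of procedures also has adverse-event checks at 1 and 12 months, which would add to the load.

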7.7 Trial assessments

Assessment will take place at baseline and then at 1, 3, and 12-months post randomisation. The 3month follow up will be the primary endpoint. All assessments will be through the survey website programmed in Qualtrics. Only if participants have not responded to email and text prompts to complete their follow ups at 3 or 12-months will they be contacted by phone and asked to provide the primary outcome measures only on the telephone. (We have found that in previous studies participants are often willing to provide these measures on the phone rather than complete the full online assessment). The results of the assessments are only to collect research data for the trial and will not be provided to medical practitioners. The only exception to that would be if a participant indicates suicide risk and asks us to provide their assessment results to their medical practitioner. They would need to give written consent for this and provide us with the contact details to do so. See risk protocol in Appendix 16.

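### The one SAE question shown looks back 3 months, so with follow-ups at 1, 3 and 12 months it leaves about months 3 to 9 outside it, although SAEs are analysed over 12 months

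*Protocol*

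**What the plan says.** Protocol 16.5 (Safety Reporting Flow Chart) gives the SAE check to be used at follow-up: "Have you experienced any health emergencies, accidents, unplanned hospital admissions in the last 3 months". Tick-boxes for cause come after it, among them self injury and taking part in the trial. The same chart makes the automatic notification depend on the participant's answer: "Website sends alert to site PI, site researcher and trial manager if AE reported and ppt ticks that its related to trial participation". A separate item asks, without a fixed recall period, "has taking part in the trial so far made you feel much worse".

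On timing, Protocol 7.7 says "Assessment will take place at baseline and then at 1, 3, and 12-months post randomisation". The row "Adverse event assessments" in Protocol 16.4 is marked yes at all three follow-ups.

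On the period to be reported, Protocol 9.3 says "The reporting period for all events and reactions will be from referral to 12month post baseline follow-up". SAP 6.10 says "The main anticipated adverse event in this trial is deliberate self-harm". It plans a Poisson or negative binomial model for the count of events and a logistic model for "the number of participants experiencing the outcome at least once during the 12-month follow-up period". SAP Table A.14 carries the same 12-month period in its title.

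**The concern.** The recall period is fixed, but the intervals between follow-ups are 1, 2 and 9 months. A 3-month look-back is longer than the first two intervals and much shorter than the third. Read as written, the question cannot supply a complete 12-month count, and its answers at month 1 can include events from before the trial.

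Two things are at stake. First, an event in the middle of follow-up is not systematically asked about together with its cause and its relation to the trial, and the related-event alert depends on that tick. Second, the count model in SAP 6.10 would treat 12 months as observed, when this source observes about half of them. The same count could also include events that are pre-randomisation or recorded twice. Other instruments in the plan have their recall fitted to the 12-month visit (LIDAS and AD-SUS in Protocol 3.7, Table 16). No such variant of the SAE question is shown.

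**Working it through.** The plan states no figure for coverage, so there is none to reproduce. The check is interval arithmetic in months from randomisation.

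**Inputs.** Recall is 3 months (Protocol 16.5). Follow-ups are at 1, 3 and 12 months (Protocol 7.7). The collection window is 14 days either side at 3 and 12 months (SAP 3.8), and 14 / 30.44 = 0.46 months. The suicide-risk questions look back 2 weeks, also 0.46 months (Protocol 16.1). AD-SUS at 12 months looks back to the 3-month interview (Protocol 3.3, Health Economics Measures; SAP 8.8).

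**Coverage of the SAE question.** A follow-up at month f covers f − 3 to f.

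| Follow-up | Recall interval | On-study part |
|---|---|---|
| 1 month | −2 to 1 | 0 to 1 |
| 3 months | 0 to 3 | 0 to 3 |
| 12 months | 9 to 12 | 9 to 12 |

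The three forms ask about 3 × 3 = 9 months in total. Of these, 2 lie before randomisation and 1 (month 0 to 1) is asked about twice, which leaves 9 − 2 − 1 = 6 distinct on-study months. So 6 of 12 are covered (50%), and months 3 to 9 are not.

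**With visit windows.** Gap = (v12 − 3) − v3, where v3 and v12 are the actual visit times.
- Nominal: (12 − 3) − 3 = 6.0 months.
- Shortest: (11.54 − 3) − 3.46 = 5.08 months, which is 5.08 / 11.54 = 44% of follow-up.
- Longest: (12.46 − 3) − 2.54 = 6.92 months, which is 6.92 / 12.46 = 56% of follow-up.

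**Missed 3-month visit.** Only 0 to 1 and 9 to 12 are covered, so the gap is months 1 to 9, or 8 months. Protocol 7.7 limits the telephone fallback to the primary outcome measures. As described, then, a participant reached only by telephone at month 3 would be in the same position.

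**What else reaches months 3 to 9.**
- AD-SUS at month 12 covers v3 to v12, hence the whole gap. As described in Protocol 3.3 it records service contacts, stays and medication, not cause or relatedness.
- The 2-week risk questions at month 12 start at 11.54 (11.08 at the earliest), and those at month 3 end where the gap begins. The overlap is 0 in every window combination. They ask about thoughts, intention and plans.
- The questions on treatment and services received since the last assessment (Protocol 8, usual practice control) also reach the gap, for care received.
- The item on the trial so far (16.5) and the open harm questions at 3 and 12 months (Protocol, Adverse events, Participant welfare and safety) prompt for worsening linked to the trial or the app.

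**Recall fitted to the visit.** The intervals become 0 to 1, 1 to 3 and 3 to 12, giving 1 + 2 + 9 = 12 of 12 months with no overlap.

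**The case against.** The strongest reply is that the question is one source among several. The Protocol's section on participant welfare names hospitalisation and emergency-care items in AD-SUS as an adverse-event source, and those reach back to month 3. Trial-related harm is prompted by the so-far item and the open questions. LIDAS has a 12-month recall at month 12, although it covers the diagnostic criteria for depression and not acts. Participants can report at any time, and Protocol 9.4 has site researchers check for events at follow-up. All of this stands. A reader might infer that no SAE from months 3 to 9 can be captured, or that one without service contact is counted only if volunteered. The documents do not support either reading.

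A second reply is that the evidence is one line in a flow chart. The fielded 12-month form is not in the documents and may differ. Protocol 12 mentions an SAE form in the eCRF that is not shown, so a missing date in the flow chart does not prove that dates go unrecorded. This too stands, and it makes the remedy conditional. It does not remove the mismatch between the stated recall and the stated analysis period, and SAP 6.10 does not say which sources feed the SAE counts.

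A third reply concerns self-harm. Self injury is a cause box under a stem about emergencies, accidents and admissions. Self-harm that involved none of these would not clearly be elicited at any recall length. That is correct, and it limits what a change of recall can achieve.

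**Conclusion.** As worded, the SAE question covers half of the 12-month period over which SAEs are to be reported and analysed. The gap is 6.0 months nominally, 5.1 to 6.9 with the SAP 3.8 windows, and 8 months after a missed 3-month visit. SAP 6.1 describes a different collection window of just under 3 weeks; using it would alter the range but not the nominal gap. For the gap period, cause and relatedness are not systematically asked, nor are emergencies or accidents (including self-injury) that led to no service contact. At month 1 the wording admits events from up to about 2 months before randomisation and duplicates part of the 3-month recall.

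The conclusion assumes that the flow-chart wording is used unchanged at every follow-up. The figures describe coverage by one question. The number of SAEs missed cannot be derived from the documents. A reader might also infer that under-reporting is equal across arms because the wording is the same in each, or the opposite, that it biases the comparison. Neither can be shown: the question is identical by arm, but some reports are volunteered, and SAP 3.9 accepts that participants may deduce their arm. Months 0 to 3, when most app use is expected, are covered. This is an inexpensive improvement worth making, not a failure of safety monitoring as a whole.

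**What to change.** First check the fielded 12-month form. Unless it already differs:

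- At each follow-up, ask about the period since the last completed assessment, or since joining if there is none. Completed should mean an assessment at which the SAE question was answered.
- Record the date of each event, so that the 12-month period can be applied and pre-randomisation or duplicate events removed before the count model is fitted.
- State in SAP 6.10 that the AD-SUS hospital and emergency items are a supplementary SAE source for months 3 to 12.
- For 12-month forms already completed with the 3-month wording, report that the SAE question covers months 0 to 3 and 9 to 12 only.
- If self-harm outside emergencies, accidents and admissions is meant to be counted, name it in the question. The new recall closes the time gap only.

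The cost is a small edit and a date field in an online form in four languages, a sentence in the SAP, and some work to match AD-SUS answers to SAE reports. Sponsor and ethics committee approval is needed under Protocol 13.10. The drawback is a longer recall at 12 months, with some recall error. AD-SUS already accepts that recall.
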